1.7. PRIOR AND CONCOMITANT THERAPY

1.7.1. Prior Therapy

Participants who received prior cell therapy of any kind will be excluded from the study (see [Section 1.4.2](#)).

Rilutek (riluzole), Nuedexta (dextromethorphan hydrobromide and quinidine sulfate), and Radicava or Radicut (edaravone) are the only Food and Drug Administration (FDA)-approved drugs for participants with ALS (Nuedexta is approved only to treat pseudobulbar affect that occurs in some participants with ALS). Study participants must be on a stable dose of riluzole for at least 30 days prior to screening, or not on riluzole at all with no plans to begin therapy with riluzole for the duration of the study. Participants may not have taken Edaravone within 30 days of screening and must not plan to begin therapy with edaravone for the duration of the study. Study participants who begin an excluded medication during the study period will be discontinued from treatment. In order to minimize the amount and impact of missing data, study investigators will make all reasonable efforts to collect key efficacy and safety data on participants who discontinue treatment or discontinue from the study.

All medications taken prior to the first transplantation will be recorded as Prior medications.

1.7.2. Concomitant Therapy

Concomitant medications are those given to the subject during or after the first transplantation. All concomitant medications will be recorded.

Participants who were on a stable dose of riluzole for at least 30 days prior to screening will continue taking riluzole prior to study enrolment, unless requiring discontinuation during the study for standard side-effects.

In addition, the use of non-invasive procedures including continuous positive airway pressure and diaphragmatic pacing systems will be recorded.

1.8. SAFETY REPORTING

For this study, AEs and SAEs will be collected from the screening visit through the end of the study period as detailed in [Section 1.8.1](#).

1.8.1. Adverse Events definitions and reporting

Standard definitions for AEs are provided in this section for informational purposes.

1.8.1.1. Adverse Event (21 CFR 312.32(a))

AE means any untoward medical occurrence associated with the use of a drug in humans, whether or not considered drug related. An AE can be any unfavorable and unintended sign (e.g., an abnormal laboratory finding), symptom, or disease temporally associated with the use of a drug, without any judgment about causality.

Within this investigation, adverse events also encompass procedurally related observations based upon physical examination of the patient, or laboratory assessments or spontaneously reported by the subject which are temporally associated with the administration of study medication.

For adverse events requiring medical interventions such as surgeries, diagnostic procedures and therapeutic procedures it is recommended that these be recorded as treatment of the adverse event or action taken rather than an additional adverse event

1.8.1.2. Serious Adverse Event (21 CFR 312.32(a))

An AE or suspected adverse reaction is considered “serious” (SAE) if, in the view of either the Investigator or Sponsor, it results in any of the following outcomes:

- Death
- Life-threatening (an AE or suspected adverse reaction is considered “life-threatening” if, in the view of either the Investigator or Sponsor, its occurrence places the subject or subject at immediate risk of death. It does not include an AE or suspected adverse reaction that, had it occurred in a more severe form, might have caused death)
- Inpatient hospitalization or prolongation of existing hospitalization excluding:
 - A visit to the emergency room or other hospital department for <24 hours that does not result in admission (unless considered an important medical event or life-threatening)
 - An elective surgery planned prior to signing informed consent

- Protocol specified admissions for planned procedures
- Admission for social circumstance that has no bearing on health status and requires no intervention (e.g., economic inadequacy, family circumstances, administrative)
- A persistent or significant incapacity or substantial disruption of the ability to conduct normal life functions
- A congenital anomaly/birth defect
- Important medical events that may not result in death, be life-threatening, or require hospitalization may require medical or surgical intervention to prevent one of the outcomes listed in this definition. Examples of such medical events include allergic bronchospasm requiring intensive treatment in an emergency room or at home, blood dyscrasias or convulsions that do not result in inpatient hospitalization, or the development of drug dependency or drug abuse.

If it is not certain that an event meets the above definitions of an SAE, the site investigators will contact the Medical Monitor to discuss.

SAEs reported through 12 weeks following the last transplantation will be entered in the study safety database and reported as such.

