1.3.2 Study Schematic

The study comprises an up to 20-week pre-treatment period including an approximately up to 12 weeks screening period, a 16-week treatment period, during which three transplantations will be performed followed by a 12-week post-treatment follow-up period (Figure 1).

Participants' bone marrow will be aspirated up to approximately 15 weeks following the first screening visit. The MSC isolation and cell propagation processes will last about 4-5 weeks and will be followed by NurOwn® (MSC-NTF cells) transplantation.

At each transplantation visits [up to about 20 weeks after the screening visit, up to 28 weeks after the screening visit (8 weeks after first transplantation) and up to 36 weeks after the screening visit (8 weeks after second transplantation)], participants will be admitted to an inpatient study unit for study procedures and will be followed for 24-72 hours post transplantation. In consideration of the COVID-19 pandemic, patients may be released from the inpatient units after observation for less than 24 hours, per Principal Investigator’s judgment of their clinical status, as the risk of prolonged stay in the hospital may outweigh the potential benefit.

Following each treatment, participants will be assessed at visits described in Table 1. After receiving the third treatment dose (at Week 16 weeks after the first transplantation), all participants will be followed for 12 weeks for evaluation of key efficacy and safety assessments.

Each participant will thus be followed for a total of up to about 48 weeks (~12 months) from the first visit (Figure 1).

[figure not shown]

Figure 1 Clinical study flowchart

Clinical study flowchart outlining the pre-treatment and screening periods, the treatment period and the post-transplant follow-up visits. RNZ: Randomization; BMA: Bone Marrow Aspiration;

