Abbreviations: ALS=Amyotrophic Lateral Sclerosis; ALFRS-R=ALS Functional Rating Scale–Revised; CMV=cytomegalovirus; CSF=cerebral spinal fluid; C-SSRS=Columbia-Suicide Severity Rating Scale; ECG=electrocardiogram; HIV=human immune deficiency virus; HBV=hepatitis B virus; HCV=hepatitis C virus; IT=intrathecal; V=visit

* SVC will be performed when permitted, following resolution of COVID-19 per institutional guidance

- 1 Driven by manufacturing availability. Prior to randomization complete a request for randomization form for Medical Monitor review and approval
- 2 ,Blood pressure, Body temperature, Pulse and respiratory rate (after sitting for at least 3 minutes)
- 3 ALS Medical History to collect type and duration of ALS symptoms and Date of Diagnosis
- 4 Every effort will be made to collect the ALSFRS-R scores in-person, however by exception it may be collected by telephone.
- 5 Hematology: Complete blood count (red blood cells with indices, white blood cells with differential and platelet count, hemoglobin, hematocrit)
- 6 Blood Biochemistry: Sodium, Potassium, Calcium, Bicarbonate, blood urea nitrogen, Creatinine, Glucose, Chloride, Magnesium, Phosphorus, total protein, triglycerides, Total cholesterol, high-density lipoprotein, low-density lipoprotein, urea, total bilirubin, aspartate aminotransferase (glutamic oxaloacetic transaminase), alanine aminotransferase (glutamic pyruvic transaminase), alkaline phosphatase, uric acid
- 7 Coagulation: Prothrombin time (PT), Partial thromboplastin (PTT).
- 8 Blood samples for analysis of T regulatory cells will be collected at V6, V7 and V8 only
- 9 Urinalysis - Specific Gravity, pH, glucose, protein, ketones, blood
- 10 Bone marrow derived mononuclear cells or MSC derived from the Bone Marrow aspirated at Visit 5, will be collected for DNA isolation and genetic analyses
- 11 A more flexible window may be applied to the key study visits, Randomization (V4), BMA (V5), T1 (V6), T2 (V9) and T3 (V11) that are scheduled based on manufacturing availability.

Brainstorm Cell Therapeutics		
Phase 3 Clinical Protocol BCT-002 US Amendment 2.1: March 2020	NurOwn® (MSC-NTF cells)	Page 60 of 66

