#### 6.5. Analysis Populations

During the conduct of this study starting in February 2020 the pandemic due to COVID-19 impacted the US and some of the subject in-clinic visits for intrathecal administrations, efficacy or safety assessments were either delayed or cancelled. As of finalization of this SAP the COVID-19 pandemic is still ongoing and its impact is yet unknown. All subjects who continued in the study and were intended to receive treatments are receiving them with sometimes longer duration between visits due to travel restrictions, manufacturing and clinical site constraints. Phone visits were conducted as close to the planned visits to determine if subjects had AEs or there were changes to any CMs. Since the ALSFRS-R is validated to be performed over the

phone, these were conducted as close to the planned visits as possible. Protocol deviations due to COVID-19 are being captured and will be summarized in the clinical study report (CSR).

Prior to locking the database and unblinding the study, the impact of treatment delays due to manufacturing scheduling or due to COVID-19 will be assessed on the data collected and additional modifications to the populations below may be made. In addition, sensitivity analyses may be added including/excluding data collected that may have been impacted due to COVID-19.

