## 9. SAFETY

All safety analyses will be analyzed for the Safety Population. The AEs and SAEs will be collected from the screening visit through the end of the study period.

Safety will be assessed based on the incidence of treatment emergent adverse events (TEAEs) and clinically relevant changes in vital signs, clinical laboratory assessments (hematology, serum chemistry, and urinalysis), physical and neurological examinations, ECG tests. Each safety parameter will be listed by subject.

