The relation of TEAEs to study drug will be summarized by their relatedness (definite, probable, possible, unlikely and not related).

For subjects who discontinue the study, any SAEs reported through 12 weeks following their last transplantation prior to discontinuation will be included in the safety database.

A listing will provide details of all subjects who experience a SAE, died during the study or experienced an AE that led to discontinuation from the study.

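### The end of SAE capture is stated in unreconciled ways, and the 12-week rule for study discontinuers can stop 8 or 16 weeks before Week 28

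*Protocol*

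**What the plan says.** Four statements bear on when SAE capture ends.

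- **End of study.** Protocol 1.8: "AEs and SAEs will be collected from the screening visit through the end of the study period", with a pointer to Section 1.8.1 for detail. SAP 9 repeats it: "The AEs and SAEs will be collected from the screening visit through the end of the study period".
- **Twelve weeks after the last injection, no group named.** Protocol 1.8.1.2, which lies inside the section that 1.8 points to: "SAEs reported through 12 weeks following the last transplantation will be entered in the study safety database and reported as such".
- **Twelve weeks after the last injection, study discontinuers only.** SAP 9.1.1, on what enters the safety database: "For subjects who discontinue the study, any SAEs reported through 12 weeks following their last transplantation prior to discontinuation will be included in the safety". Protocol 1.8.5.2 does much the same: after discontinuation, events the site happens to learn of within 12 weeks of the last transplant go in the AE log.
- **Every remaining scheduled visit.** Protocol 1.5.7 and footnote 12 to Protocol Table 1 require attempted telephone AE review through the rest of the study for participants who refuse further clinic visits.

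On follow-up after dosing, Protocol 1.3.2 says that after the third injection "all participants will be followed for 12 weeks for evaluation of key efficacy and safety assessments". Protocol Table 1 puts the injections at Weeks 0, 8 and 16 and Visit 14 at Week 28, with ±5 days on Weeks 8, 16 and 28. Footnote 11 adds: "A more flexible window may be applied to the key study visits", including the third injection, with no maximum. SAP 6.5 reports that participants are receiving their treatments "with sometimes longer duration between visits due to travel restrictions, manufacturing and clinical site constraints".

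**The concern.** Safety is a primary objective (Protocol 1.2.1), so each participant's observation period for serious events should be unambiguous and the same in both arms. A window tied to the last injection is shorter for anyone who receives fewer injections. One route to fewer injections exists in one arm only. Protocol 1.8.5.2 lists failure to produce enough cells as a reason to leave the study, and Protocol 1.3.1 has cells isolated and expanded only for the treatment group, then thawed and induced before each treatment. Such a failure can therefore occur between doses, and only on NurOwn. If the 12-week limit is applied to these participants while others are counted to Week 28, the SAE comparison rests on unequal observation time.

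The end-of-study rule has a different weakness. If Visit 14 stays at Week 28 when the third injection is late, follow-up after the last exposure falls below the 12 weeks that Protocol 1.3.2 states for everyone.

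Protocol 1.8.1.2 and SAP 9.1.1 also set the limit by when an SAE is reported. Read literally, an event with onset in week 11 after the last injection that the site learns of in week 13 falls outside.

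**Working it through.** **Inputs.** Injections at Weeks 0, 8 and 16; Visit 14 at Week 28; ±5 days on Weeks 8, 16 and 28 (Protocol Table 1). The 12-week limit is from Protocol 1.8.1.2 and SAP 9.1.1.

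**The plan's own figures.** Follow-up after the third injection on the nominal schedule: 28 − 16 = 12 weeks. Total participation: 20 + 16 + 12 = 48 weeks. Both match Protocol 1.3.2.

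**12-week rule against end of study.** With the last injection at week w, the rule ends at w + 12, and the gap to Week 28 is 28 − (w + 12).

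| Last injection | 12-week rule ends | Gap to Week 28 | Gap with visit windows |
|---|---|---|---|
| First (w = 0) | Week 12 | 16 weeks | 15.3 to 16.7 |
| Second (w = 8) | Week 20 | 8 weeks | 6.6 to 9.4 |
| Third (w = 16) | Week 28 | 0 | −1.4 to 1.4 |

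Window column, second injection: the shortest interval to Visit 14 is (196 − 5) − (56 + 5) = 130 days and the longest is (196 + 5) − (56 − 5) = 150 days. That is 18.6 and 21.4 weeks; subtracting 12 gives 6.6 and 9.4. For the first injection the intervals are 191 and 201 days.

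**Who falls under which statement.**

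- Completers with the third injection at Week 16: all statements agree.
- Stopped dosing, still in the study: covered to study end by Protocol 1.8 and SAP 9, unless Protocol 1.8.1.2 is read as a cut-off.
- Left the study: SAP 9.1.1 and Protocol 1.8.5.2 give 12 weeks after the last injection. Protocol 1.5.7 and footnote 12 give AE contact through all remaining visits if the person refuses clinic visits. Protocol 1.8.5.2 itself asks for telephone follow-up over the remaining visits before it states the 12-week limit.
- Randomized but never transplanted: the 12-week rule has no starting point. These participants are outside the Safety Population (SAP 6.5.1).

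**Late third injection, end-of-study rule, Visit 14 held at Week 28.** Inside the printed windows the shortest follow-up is (196 − 5) − (112 + 5) = 74 days (10.6 weeks) and the longest is 94 days (13.4 weeks). For a delay of d weeks, follow-up is 12 − d: delays of 1, 2, 4 or 8 weeks leave 11, 10, 8 or 4 weeks. These values of d are assumptions, because the documents state no maximum and no observed length.

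**The case against.** The case against is substantial, and much of it stands.

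- **Stopping dosing is not leaving the study.** A reader might infer that anyone who stops injections early loses 8 to 16 weeks of SAE capture. The documents do not support that. SAP 9.1.1 confines the 12-week rule to study discontinuers, Protocol 1.8 and SAP 9 cover everyone else to study end, and Protocol 1.7.1 asks sites to keep collecting key safety data after treatment stops.
- **The 12-week sentence includes; it does not expressly exclude.** It says what will be entered, not that later events are dropped. Section 1.8.1 introduces its definitions as informational. Protocol 1.8.2 requires all SAEs to be reported within 24 hours of the investigator learning of them, and the TEAE definition in SAP 9.1.1 has no upper time limit. For people who have left, the limit also extends capture beyond study exit.
- **The two harms need opposite readings.** The 8- or 16-week gap arises only if the 12-week rule governs; the shortfall after a late third injection arises only if end of study governs and Visit 14 does not move. A reader who counts both as consequences of one plan goes too far.
- **Visit 14 may move.** Protocol 1.3.2 and 1.3.5 tie about 12 weeks of follow-up to the last dose, and the synopsis allows visits to be rescheduled. The 74-day figure puts both windows at opposite extremes.
- **Imbalance between arms is not shown.** No rate of cell failure between doses is given.

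What remains is that no text says which end-point governs. For study discontinuers the shorter limit is written into both documents, alongside a requirement for contact through the remaining visits. The existing telephone contact softens the problem but covers only those who refuse clinic visits.

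**Conclusion.** The point holds as an unreconciled definition with a possible cost to the safety comparison. The end-points coincide only when the third injection is at Week 16. For a study discontinuer whose last injection was the first or second, the 12-week rule ends 16 or 8 weeks before Week 28. For a participant who stops dosing and stays, the gap is nil unless Protocol 1.8.1.2 is read as a cut-off. Differential loss in the NurOwn arm through failed cell production is possible from the design, but its frequency is unknown, so it is a risk and not a shown bias. The shortfall after a late third injection is conditional on end of study governing and Visit 14 staying at Week 28, which the documents leave open. It is about 1.4 weeks (84 − 74 = 10 days) at the edge of the printed windows and of unknown size beyond them. The text should be corrected before the safety data are summarized; nothing here shows that SAEs have been lost.

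**What to change.** Reconcile Protocol 1.3.2, 1.5.7, 1.8, 1.8.1.2, 1.8.5.2 and Table 1 footnote 12 with SAP 9 and 9.1.1, so that one rule applies to both arms:

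1. Record and analyse AEs and SAEs by **onset date**, not report date, from screening through the later of Week 28 and 12 weeks after the last transplantation. This holds whether or not dosing or study visits stopped early, as far as consent allows.
2. State how Visit 14 is timed when the third injection is late. Where it falls before 12 weeks after the last transplantation, use the existing telephone AE contact to complete the window.

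With the last injection at week w, the window ends at max(28, w + 12). That is Week 28 for w = 0, 8 or 16, and Week 28 + d for a third injection delayed by d weeks. It closes the 16- and 8-week gaps and keeps 12 weeks after a late dose. Participants never transplanted are followed to the end of the study schedule.

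The cost is wording in both documents, a few extra calls, and possibly a slightly later database lock.

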1.8.1.3. Relatedness (Causality)

Investigators will assess relatedness of AEs to study drug using the following terms:

- **Definite:** An AE that has a clear temporal association with investigational product administration (e.g., within 72 hours); provides a plausible pharmacologic explanation for the event
- **Probable:** There is a reasonable temporal association with administration of the investigational product; unlikely caused by other drugs or underlying conditions
- **Possible:** There is a plausible temporal association with the investigational product, but other etiologies are possible and relatedness to the investigational product cannot definitely be ruled out
- **Unlikely:** The temporal association with the investigational product is implausible (but not impossible). The event is likely related to other drugs or conditions
- **Not Related:** An AE with no temporal association with the investigational product but rather related to other etiologies such as concomitant medications or conditions or subject's known clinical state; subject has not received investigational product.

1.8.1.4. Severity (Intensity)

The severity of an AE will be graded on a scale: mild, moderate, severe, as defined below:

- **Mild:** Asymptomatic or mild symptoms, clinical or diagnostic observations only; intervention not indicated

- **Moderate:** Minimal, local or non-invasive intervention indicated; interferes with age-appropriate activities of daily living
- **Severe:** Disabling; unable to carry out age-appropriate activities of daily living
- **Potentially Life-Threatening:** Medical or operative intervention indicated to prevent permanent impairment, persistent disability, or death.

1.8.1.5. Follow-Up of AEs

After the initial recording of an AE, the Investigator shall proactively follow the subject. Any non-serious AEs that are still on-going at the end of the study shall be reviewed to determine if further follow-up is required. The Investigator will document on the eCRF any/all on-going non-serious AEs that will not be followed further after the subject exits the study. If in doubt, the Investigator shall consult the study Medical Monitor.

All SAEs shall be followed until resolution, until the condition stabilizes, or until the subject is lost to follow-up, or otherwise explained. Once the SAE is resolved, the corresponding AE eCRF page shall be updated. Additionally, any relevant laboratory test reports, consultation reports from other health care professionals, discharge summaries, or other information that has been gathered about the event shall be transmitted to the Sponsor.

The Sponsor may request that the Investigator perform or arrange for the conduct of supplemental measurements and/or evaluations to elucidate as fully as possible the nature and/or causality of any AE.

1.8.1.6. Outcome

The following terms will be used during this study:

- Fatal
- Not Recovered/not resolved
- Recovering/resolving
- Recovered/resolved
- Recovered/resolved with sequelae
- Unknown

1.8.1.7. Clinically Significant Laboratory Abnormalities

Any laboratory abnormalities deemed clinically significant by the Investigator shall be reported on the AE eCRF. A clinically significant abnormality is a confirmed abnormality (by repeat test) that is changed sufficiently from screening visit so that in the judgment of the Investigator a change in management is warranted. This alteration may include: monitoring the laboratory test further, initiating other diagnostic tests or procedures, changing ongoing treatment, or administering new treatment. Whenever possible, the etiology of the abnormal finding (e.g., anemia) will be recorded on the eCRF. Repeated additional tests and/or other evaluations

required to establish the significance and etiology of an abnormal result shall be obtained when clinically indicated.

